7.4. Body Weight, Height, BMI and Vital Signs

Absolute value and change from baseline in vital signs (systolic blood pressure [SBP], diastolic blood pressure [DBP] and pulse) at each visit will be summarized for the Safety Analysis Set using descriptive statistics by treatment cohort for each postbaseline analysis window. In the case of multiple values in an analysis window, data will be selected for analysis as described in Section 3.8.3. No inferential statistics will be generated.

A listing of height (at screening), body weight, and BMI, and a listing of SBP, DBP, pulse, respiration and temperature will be provided.

7.5. Electrocardiogram (ECG) Results

Absolute value and change from baseline in PR interval, QRS interval, QT interval and QTcF at each visit will be summarized for the Safety Analysis Set using descriptive statistics by treatment cohort for each postbaseline analysis window. A listing of PR interval, QRS interval, QT interval, and QTcF will be provided.

A listing of overall assessment of ECG results including description regarding clinically significant abnormalities will be provided.

7.6. Echocardiogram Results

Absolute value and change from baseline in ejection fraction, fractional shortening, left ventricular end diastolic volume (LVEDV) and left ventricular internal dimension in diastole (LVIDd) at each visit will be summarized for the safety analysis set using descriptive statistics by treatment cohort for each postbaseline visit. A shift table of diastolic function score assessment at baseline versus each on-treatment visit will be presented.

A listing of ejection fraction, fractional shortening, LVEDV, LVIDd and diastolic function score will be provided.

7.7. Other Safety Measures

A data listing will be provided for subjects who received dialysis during the study.

A data listing will be provided for subjects who become pregnant during the study.

7.8. Changes From Protocol-Specified Safety Analyses

There are no deviations from the protocol-specified safety analyses.

8. PHARMACOKINETIC (PK) ANALYSES

Steady-state PK over the dosing interval will be determined from intensive PK assessments at the Week 2 or Week 4 on-treatment visit.

Concentration of SOF (and its metabolites GS-566500 and GS-331007) and LDV in plasma will be determined using validated bioanalytical assays. The PK parameters for these analytes will be computed for all subjects with evaluable PK profiles. For each subject, the following PK parameters will be calculated, as appropriate:

Parameter	Description
AUC _{tau}	area under the concentration versus time curve over the dosing interval
C _{last}	last observed quantifiable concentration of the drug in plasma
C _{max}	maximum observed concentration of drug in plasma
C _{tau}	observed drug concentration at the end of the dosing interval
t _{1/2}	estimate of the terminal elimination half-life of the drug in plasma, calculated by dividing the natural log of 2 by the terminal elimination rate constant (λ_z)
T _{last}	time (observed time point) of C _{last}
T _{max}	time (observed time point) of C _{max}
λ_z	terminal elimination rate constant, estimated by linear regression of the terminal elimination phase of the plasma concentration of drug versus time curve

PK parameters will be estimated by application of a nonlinear model using standard noncompartmental methods (WinNonlin® software). The linear up/log down trapezoidal rule will be used in conjunction with the appropriate noncompartmental model (usually input Model 200 for oral dosing), with input values for dose, time of dose, plasma concentration, and corresponding real time values, based on drug dosing times whenever possible. In order to calculate AUC_{tau} (dosing interval = 24 h), the pre-dose concentration will also be used as the 24h concentration since these samples are obtained at steady state conditions. However, missing concentrations from scheduled PK time-points will not be imputed.

All predose sample times of less than time zero will be converted to zero. Samples below the limit of quantitation of the bioanalytical assays that occur prior to the achievement of the first quantifiable concentration will be assigned a concentration value of zero to prevent overestimation of the initial AUC. Samples that are BLQ at all other time points will be treated as missing data. The nominal time point for a key event or dosing interval (tau) may be used to permit direct calculation of AUC over specific time intervals. The appropriateness of this approach will be assessed by the pharmacokineticist on a profile-by-profile basis.

Accurate estimation of several PK parameters, such as λ_z and $t_{1/2}$, are dependent on the measured terminal elimination phase of the drug. The appropriateness of calculating these parameters will be assessed by the pharmacokineticist on a profile-by-profile basis.

Ten descriptive statistics (sample size, mean, SD, coefficient of variation [%CV], median, Q1, Q3, minimum, maximum, and geometric mean and its 95% CI) will be presented for PK concentration data and PK parameter data. For concentration values BLQ, the number of subjects with values of BLQ will be presented.

Plasma concentrations of SOF (and its metabolites GS-566500 and GS-331007) and LDV over time from the intensive PK assessments will be plotted in linear and semi-logarithmic scales as mean \pm SD and as Q1, median, and Q3 by visit.

9. SOFTWARE

SAS® Software Version 9.4. SAS Institute Inc., Cary, NC, USA.

Phoenix® WinNonlin®, Version 6.4, Pharsight Corporation, Mountain View, CA, USA.

10. SAP REVISION

Revision Date (DD MMM YYYY)	Section	Summary of Revision	Reason for Revision

11. APPENDICES

- Appendix 1. Schedule of Assessments for Cohort 3
- Appendix 2. Tables, Figures, and Listings

Appendix 1. Schedule of Assessments for Cohort 3

Study Procedure	Screen ^a	Day 1 ^b	Treatment Visits ⁱ							Post-Treatment Visits ^j			ET ^c
			Week 1	Week 2	Week 4	Week 6	Week 8	Week 10	Week 12	Week 4	Week 12	Week 24	
Written Informed Consent	X												
Medical History	X												
HCV RNA Genotype	X												
IL28B Genotyping	X												
HbA1c	X												
HCV, HBV, HIV Serology	X												
TSH	X												
Physical Exam, including Vital Signs ^d	X	X	X	X	X	X	X	X	X	X	X	X	X
12-lead ECG	X	X			X		X		X	X	X	X	X
Echocardiogram	X									X			
Height	X												
Weight	X												
Hematology	X	X	X	X	X	X	X	X	X	X	X	X	X
Coagulation (PT, PTT, and INR)	X	X				X				X			X
Chemistry	X	X	X	X	X	X	X	X	X	X	X	X	X
HCV RNA Viral Load	X	X	X	X	X	X	X	X	X	X	X	X	X
HCV RNA Sequencing		X	X	X	X	X	X	X	X	X	X	X	X

Study Procedure	Screen ^a	Day 1 ^b	Treatment Visits ⁱ							Post-Treatment Visits ^j			ET ^c
			Week 1	Week 2	Week 4	Week 6	Week 8	Week 10	Week 12	Week 4	Week 12	Week 24	
Serum Pregnancy Test ^e	X	X			X		X		X	X	X	X	X
Creatinine Clearance	X												
Optional Pharmacogenetic Sample ^k		X											
Intensive PK				X ^f	X ^f								
Trough PK Sample ^g			X			X	X	X	X				X
Archive Plasma Sample		X	X	X	X	X	X	X	X	X	X	X	X
Study Drug Administration		X	Weeks 1-12										
Review Dosing Diary/ Perform Accountability ^h			X	X	X	X	X	X	X				
AEs/Concomitant Meds	X	X	X	X	X	X	X	X	X	X	X	X	X

a Screening evaluations must be completed within 42 days prior to Day 1.

b Day 1 tests and procedures must be completed prior to administration of the first dose of study drugs

c Within 72 hours of permanently discontinuing study drug.

d Full PE at Day 1 and ET visits only; symptom-directed PE at all other timepoints. Vital signs include blood pressure, pulse, respiration rate, and temperature

e Females of childbearing potential only. To confirm eligibility at Day 1, a urine pregnancy test may be collected for subjects able to pass urine. For subjects unable to pass urine, a serum pregnancy test at Day 1 must be performed at a local lab prior to dosing to confirm eligibility along with sample collected and send to central lab. During post-treatment of the study, serum or urine pregnancy testing will occur every month during non-clinic post treatment visits. The subject will be contacted by telephone to confirm that pregnancy testing has been performed post-treatment during non-clinic visits.

f Intensive plasma PK evaluations will be assessed at the following timepoints: 0 (predose -5 minutes), 0.25, 0.5, 1, 2, 4, 6, 8, 10, and 12 hours postdose once either on Week 2 **OR** 4, per investigator discretion.

g Trough plasma PK samples will be drawn prior to dosing.

h Dosing Diaries will be completed for all non-observed doses and will be reviewed at every visit. Unused study drug will be returned to perform study drug accountability in the original container at each visit following Day 1 for study drug compliance assessment.

- i A window of ± 2 days is allowed for the treatment visits on weeks 1, 2, and 12. A window of ± 4 days is allowed for the treatment visits weeks, and 4-10. Subjects who cannot complete their study visit per the visit schedule should ensure they do not run out of study drug prior to their next study visit. Compliance is critical to ensure adequate drug exposure.
- j A window of ± 7 days is allowed for the post treatment visits.
- k The sample should be collected on Day 1 prior to dosing, but may be collected at any time during the study or at a separate post-study visit, if necessary.

Appendix 2. Tables, Figures, and Listings

Table Number	Title	Analysis Set
15.8.1.1	Subjects Enrolled and Treated by Country and Investigator	Safety Analysis Set
15.8.1.2	Subject Disposition	Screened Subjects
15.8.1.3	Reasons for Screen Failure	Screened Subjects
15.8.3	Demographics and Baseline Characteristics	Safety Analysis Set
15.8.4	Adherence to Study Drug	Safety Analysis Set
15.9.1	SVR12	Full Analysis Set
15.9.2.1	Virologic Outcomes	Full Analysis Set
15.9.2.2	SVR by Visit During Posttreatment Follow Up	Full Analysis Set
15.9.2.3	Concordance between SVR12 and SVR24	Full Analysis Set
15.9.2.4	Proportion of Subjects with HCV RNA Less than LLOQ (15 IU/mL) While on Treatment by Visit	Full Analysis Set
15.9.2.5	HCV RNA (\log_{10} IU/mL) and Change from Baseline by Visit Through End of Treatment	Full Analysis Set
15.9.2.6	Proportion of Subjects with ALT Normalization by Visit	Full Analysis Set with ALT>ULN at Baseline
15.10.1.1.1	Individual Data and Summary Statistics of Plasma Intensive Concentration (ng/mL) at Protocol-Specified Sampling Times by Visit	SOF PK Analysis Set
15.10.1.1.2	Individual Data and Summary Statistics of Plasma Intensive Concentration (ng/mL) at Protocol-Specified Sampling Times by Visit	GS-566500 PK Analysis Set
15.10.1.1.3	Individual Data and Summary Statistics of Plasma Intensive Concentration (ng/mL) at Protocol-Specified Sampling Times by Visit	GS-331007 PK Analysis Set
15.10.1.1.4	Individual Data and Summary Statistics of Plasma Intensive Concentration (ng/mL) at Protocol-Specified Sampling Times by Visit	LDV PK Analysis Set
15.10.1.2.1	Individual Estimate and Summary Statistics for Pharmacokinetic Parameters by Visit	SOF PK Analysis Set
15.10.1.2.2	Individual Estimate and Summary Statistics for Pharmacokinetic Parameters by Visit	GS-566500 PK Analysis Set
15.10.1.2.3	Individual Estimate and Summary Statistics for Pharmacokinetic Parameters by Visit	GS-331007 PK Analysis Set
15.10.1.2.4	Individual Estimate and Summary Statistics for Pharmacokinetic Parameters by Visit	LDV PK Analysis Set
15.11.1	Duration of Exposure to Study Regimen	Safety Analysis Set
15.11.2.1.1	Adverse Events: Brief Summary	Safety Analysis Set
15.11.2.1.2	All Treatment-Emergent Adverse Events	Safety Analysis Set
15.11.2.1.3	All Treatment-Emergent Adverse Events by Preferred Term	Safety Analysis Set

Table Number	Title	Analysis Set
15.11.2.1.4	Treatment-Emergent Non-Serious AEs Occurring in At Least 5% of Subjects	Safety Analysis Set
15.11.2.2.1	Grade 3 or 4 Treatment-Emergent Adverse Events	Safety Analysis Set
15.11.2.2.2	Grade 2, 3, or 4 Treatment-Emergent Adverse Events	Safety Analysis Set
15.11.2.3.1	Treatment-Emergent Treatment-Related Adverse Events	Safety Analysis Set
15.11.2.3.2	Treatment-Emergent Treatment-Related Adverse Events by Preferred Term	Safety Analysis Set
15.11.2.3.3	Grade 3 or 4 Treatment-Emergent Treatment-Related Adverse Events	Safety Analysis Set
15.11.2.3.4	Grade 2, 3, or 4 Treatment-Emergent Treatment-Related Adverse Events	Safety Analysis Set
15.11.4.1	Treatment-Emergent Serious Adverse Events	Safety Analysis Set
15.11.4.3	Treatment-Emergent Treatment-Related Serious Adverse Events	Safety Analysis Set
15.11.5.1	Adverse Events Leading to Premature Discontinuation of Study Drug	Safety Analysis Set
15.11.5.2	Adverse Events Leading or Interruption of Study Drug	Safety Analysis Set
15.11.6.1.1	Hemoglobin (g/dL) and Change from Baseline by Visit	Safety Analysis Set
15.11.6.1.2	Subjects with Postbaseline Hemoglobin < 10 g/dL and < 8.5 g/dL	Safety Analysis Set
15.11.6.1.3	Reticulocytes (x10 ³ /uL) and Change from Baseline by Visit	Safety Analysis Set
15.11.6.1.4	WBC (x10 ³ /uL) and Change from Baseline by Visit	Safety Analysis Set
15.11.6.1.5	Neutrophils (x10 ³ /uL) and Change from Baseline by Visit	Safety Analysis Set
15.11.6.1.6	Lymphocytes (x10 ³ /uL) and Change from Baseline by Visit	Safety Analysis Set
15.11.6.1.7	Platelets (x10 ³ /uL) and Change from Baseline by Visit	Safety Analysis Set
15.11.6.2.1	ALT (U/L) and Change from Baseline by Visit	Safety Analysis Set
15.11.6.2.2	AST (U/L) and Change from Baseline by Visit	Safety Analysis Set
15.11.6.2.3	Total Bilirubin (mg/dL) and Change from Baseline by Visit	Safety Analysis Set
15.11.6.2.4	Alkaline Phosphatase (U/L) and Change from Baseline by Visit	Safety Analysis Set
15.11.6.2.5	Creatinine (mg/dL) and Change from Baseline by Visit	Safety Analysis Set
15.11.6.2.6	Estimated Glomerular Filtration Rate by Cockcroft-Gault (mL/min) and Change from Baseline by Visit	Safety Analysis Set
15.11.6.3	INR and Change from Baseline by Visit	Safety Analysis Set
15.11.6.4.1	Treatment-Emergent Graded Laboratory Abnormalities	Safety Analysis Set
15.11.6.4.2	Treatment-Emergent Grade 3 or 4 Laboratory Abnormalities	Safety Analysis Set
15.11.7.1.1	Systolic Blood Pressure (mmHg) and Change from Baseline by Visit	Safety Analysis Set
15.11.7.1.2	Diastolic Blood Pressure (mmHg) and Change from Baseline by Visit	Safety Analysis Set
15.11.7.1.3	Pulse (bpm) and Change from Baseline by Visit	Safety Analysis Set
15.11.7.3	Concomitant Medications	Safety Analysis Set

Table Number	Title	Analysis Set
15.11.9.1	Summary of On-Treatment ECG Abnormality	Safety Analysis Set
15.11.9.2.1	PR Interval (ms) and Change from Baseline by Visit	Safety Analysis Set
15.11.9.2.2	QRS Interval (ms) and Change from Baseline by Visit	Safety Analysis Set
15.11.9.2.3	QT Interval (ms) and Change from Baseline by Visit	Safety Analysis Set
15.11.9.2.4	QTcF (ms) and Change from Baseline by Visit	Safety Analysis Set
15.11.10.1.1	Echocardiogram: Ejection Fraction (%) and Change from Baseline by Visit	Safety Analysis Set
15.11.10.1.2	Echocardiogram: Fractional Shortening (%) and Change from Baseline by Visit	Safety Analysis Set
15.11.10.2.1	Echocardiogram: LVEDV (mL) and Change from Baseline by Visit	Safety Analysis Set
15.11.10.2.2	Echocardiogram: LVIDd (cm) and Change from Baseline by Visit	Safety Analysis Set
15.11.10.3	Echocardiogram: Shift Table of Baseline versus On-Treatment Diastolic Function Score Assessment by Visit	Safety Analysis Set

Figure Number	Title	Analysis Set
15.8.1	Subject Disposition	Screened Subjects
15.9.2.3	Proportion of Subjects with SVR (HCV RNA < LLOQ) by Posttreatment Visit	Full Analysis Set
15.9.2.4	Proportion of Subjects with HCV RNA < LLOQ While on Treatment by Visit	Full Analysis Set
15.10.1.1.1	Mean (SD) Plasma Concentration - Time (0 hour - 12 hours) Profiles by Visit	SOF PK Analysis Set
15.10.1.1.2	Mean (SD) Plasma Concentration - Time (0 hour - 12 hours) Profiles by Visit	GS-566500 PK Analysis Set
15.10.1.1.3	Mean (SD) Plasma Concentration - Time (0 hour - 12 hours) Profiles by Visit	GS-331007 PK Analysis Set
15.10.1.1.4	Mean (SD) Plasma Concentration - Time (0 hour - 12 hours) Profiles by Visit	LDV PK Analysis Set
15.10.1.1.5	Median (Q1, Q3) Plasma Concentration - Time (0 hour - 12 hours) Profiles by Visit	SOF PK Analysis Set
15.10.1.1.6	Median (Q1, Q3) Plasma Concentration - Time (0 hour - 12 hours) Profiles by Visit	GS-566500 PK Analysis Set
15.10.1.1.7	Median (Q1, Q3) Plasma Concentration - Time (0 hour - 12 hours) Profiles by Visit	GS-331007 PK Analysis Set
15.10.1.1.8	Median (Q1, Q3) Plasma Concentration - Time (0 hour - 12 hours) Profiles by Visit	LDV PK Analysis Set

Listing Number	Title	Analysis Set
16.1.6	Lot Number and Kit ID	Safety Analysis Set
16.2.1.3	Subject Disposition	Safety Analysis Set
16.2.1.4	Reasons for Screen Failure	Subjects Screened But Not Enrolled
16.2.2.1	Eligibility Criteria Deviations	Safety Analysis Set
16.2.4.1	Subject Demographics and Baseline Characteristics	Safety Analysis Set
16.2.4.2	Cirrhosis Determination	Safety Analysis Set
16.2.4.3.1	Medical History	Safety Analysis Set
16.2.4.3.2	Prior HCV Treatment and Response	Safety Analysis Set
16.2.4.4	Prior and Concomitant Medications	Safety Analysis Set
16.2.5.1	Study Drug Administration	Safety Analysis Set
16.2.5.2	Study Drug Accountability and Adherence	Safety Analysis Set
16.2.5.3	Plasma PK Sampling Details and PK Concentrations	PK Analysis Set
16.2.6.1	HCV RNA (log ₁₀ IU/mL) and Change from Baseline	Safety Analysis Set
16.2.6.2	Subjects with Virologic Failure	Safety Analysis Set
16.2.6.3	Subjects with 'Other' Virologic Outcome	Safety Analysis Set
16.2.6.4	Subjects with Relapse After Posttreatment Week 12	Safety Analysis Set
16.2.7.1	All Adverse Events	Safety Analysis Set
16.2.7.2.1	Deaths	Safety Analysis Set
16.2.7.3	Serious Adverse Events	Safety Analysis Set
16.2.7.4	Grade 3 or 4 Adverse Events	Safety Analysis Set
16.2.7.5	Adverse Events Leading to Premature Discontinuation from Any Study Drug	Safety Analysis Set
16.2.8.1.1	Subjects with Postbaseline Hemoglobin < 10 g/dL and < 8.5 g/dL	Safety Analysis Set
16.2.8.1.2	Central Laboratory (Covance) Reference Ranges	Safety Analysis Set
16.2.8.1.3	Subjects with Treatment-Emergent Grade 3 or 4 Laboratory Abnormalities	Safety Analysis Set
16.2.8.1.4	Screen Labs: HBsAg, Anti-HIV Ab, Anti-HCV Ab, HbA1c, and Serum Beta hCG	Safety Analysis Set
16.2.8.1.5.1	Hematology: Hematocrit, Hemoglobin, Reticulocyte Count, MCV, RBC, WBC, and Platelets	Safety Analysis Set
16.2.8.1.5.2	Hematology: WBC, Neutrophils, and Lymphocytes	Safety Analysis Set
16.2.8.1.5.3	Hematology: Eosinophils, Basophils, and Monocytes	Safety Analysis Set

Listing Number	Title	Analysis Set
16.2.8.1.6.1	Chemistry: Sodium, Potassium, Serum Creatinine, Estimated GFR (Cockcroft-Gault), and Glucose	Safety Analysis Set
16.2.8.1.6.2	Chemistry: AST, ALT, Total Bilirubin, Direct Bilirubin, Alkaline Phosphatase, GGT, and Albumin	Safety Analysis Set
16.2.8.1.7	Coagulation and Other Laboratory Tests: INR, APTT, and TSH	Safety Analysis Set
16.2.8.2.1	Vital Signs	Safety Analysis Set
16.2.8.2.2	Height, Weight, and BMI	Safety Analysis Set
16.2.8.2.3.1	Overall Assessment of Electrocardiogram Results	Safety Analysis Set
16.2.8.2.3.2	Electrocardiogram measurements	Safety Analysis Set
16.2.8.3.1	Echocardiogram Results	Safety Analysis Set
16.2.8.3.2	Echocardiogram: Ejection Fraction and LVEDV	Safety Analysis Set
16.2.8.4	Dialysis	Safety Analysis Set
16.2.8.5	Pregnancy	Safety Analysis Set
16.2.8.6	Comments	Safety Analysis Set

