8.1.2. Primary Endpoint

The primary safety endpoints include incidences of AEs, laboratory, 12-lead ECG, and vital sign abnormalities.

The primary PK endpoints are parameters AUC_{τ} , C_{\max} , and C_{τ} for analytes SOF, its metabolites, LDV and RBV as applicable.

The primary efficacy endpoint is SVR12 (HCV RNA < LLOQ 12 weeks after discontinuation of therapy).

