8.2.1.2. Safety

The primary analysis set for safety analyses will be the Safety Analysis Set which includes subjects who received at least one dose of study drug.

Treatment-emergent data will be analyzed and defined as data collected from the first dose of study drug through the date of the last dose of study drug plus 30 days.

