8.5. Safety Analysis

Safety will be evaluated by assessment of clinical laboratory tests, physical examinations, vital signs measurements, at various time points during the study, and by the documentation of AEs.

All safety data collected on or after the first dose of study drug administration up to 30 days after the last dose of study drug will be summarized according to the study drug received. Safety endpoints will be summarized as the number (proportion) of subjects with events or abnormalities for categorical data or as an 8-number summary (n, mean, standard deviation, minimum, Q1, median, Q3, maximum) for continuous data.

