3.8.2. Analysis Visit Windows

Subject visits might not occur on protocol-specified days. Therefore, for the purpose of analysis, observations will be assigned to analysis windows. Analysis windows are defined for HCV RNA, vital signs, safety laboratory, and electrocardiogram (ECG).

In general, the baseline value will be the last nonmissing value on or prior to the first dose date of study drug.

HCV RNA, vital signs, safety laboratory and ECG data collected up to the last dose date + 2 days are considered to be on-treatment data and HCV RNA, vital signs, safety laboratory and ECG data collected after the last dose date + 2 days are considered posttreatment data.

The analysis windows for on-treatment HCV RNA, vital signs, and safety laboratory data are provided in [Table 3-1](#). The analysis windows for on-treatment ECG data are provided in [Table 3-2](#).

Table 3-1. Analysis Windows for On-treatment HCV RNA, Vital Signs and Safety Laboratory Data

Nominal Visit	Nominal Day	Lower Limit	Upper Limit
Baseline	1	(none)	1
Week 1	7	2	11
Week 2	14	12	21
Week 4	28	22	35
Week 6	42	36	49
Week 8	56	50	63
Week 10	70	64	77
Week 12	84	78	≥ 85

Table 3-2. Analysis Windows for On-treatment ECG Data

Nominal Visit	Nominal Day	Lower Limit	Upper Limit
Baseline	1	(none)	1
Week 4	28	2	42
Week 8	56	43	70
Week 12	84	71	≥ 85

HCV RNA, vital signs, safety laboratory and ECG data collected after the last dose date + 2 days will be assigned to the posttreatment follow-up (FU) visits. Visit windows will be calculated from the last dose date (ie, FU Day = collection date minus the last dose date) as shown in [Table 3-3](#).

Table 3-3. Analysis Windows for Posttreatment HCV RNA, Vital Signs, Safety Laboratory and ECG Data

Nominal FU ^a Visit	HCV RNA			Vital Signs, Safety Laboratory and ECG Data ^b		
	Nominal FU Day	Lower Limit	Upper Limit	Nominal FU Day	Lower Limit	Upper Limit
FU-4	28	21	69	28	3	30
FU-12	84	70	146		NA	
FU-24	168	147	190		NA	

^a FU-x visit = posttreatment Week-x follow-up visit.

^b Vital signs and safety laboratory data will be summarized only for the FU-4 visit (up to 30 days after last dose).

3.8.3. Selection of Data in the Event of Multiple Records in an Analysis Visit Window

Depending on the statistical analysis method, single values may be required for each analysis window. For example, change from baseline by visit usually requires a single value, whereas a time-to-event analysis would not require 1 value per analysis window.

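### The only planned count of ECG abnormalities, a primary safety endpoint, appears to stop at last dose + 2 days, although the protocol summarises safety data to last dose + 30 days

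*SAP*

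**What the plan says.** **Protocol.** Section 8.1.2 names the endpoint: "The primary safety endpoints include incidences of AEs, laboratory, 12-lead ECG, and vital sign abnormalities". Section 8.2.1.2 defines treatment-emergent data as "data collected from the first dose of study drug through the date of the last dose of study drug plus 30 days". Section 8.5 applies the same period to the summaries: "All safety data collected on or after the first dose of study drug administration up to 30 days after the last dose of study drug".

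**SAP (Cohort 3 only).** Section 3.8.2 states: "HCV RNA, vital signs, safety laboratory and ECG data collected up to the last dose date + 2 days are considered to be on-treatment data". For anything later: "safety laboratory and ECG data collected after the last dose date + 2 days will be assigned to the posttreatment follow-up (FU) visits". Table 3-3 gives ECG data an FU-4 window of follow-up (FU) days 3 to 30. Section 7.5 plans summaries of PR, QRS, QT and QTcF by window, plus listings. It mentions no incidence table and does not define an ECG abnormality. The one table that counts abnormalities is found only in Appendix 2, as Table 15.11.9.1, "Summary of On-Treatment ECG Abnormality". Section 7.8 closes the safety chapter: "There are no deviations from the protocol-specified safety analyses".

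**The concern.** Two observation periods apply to one primary safety endpoint. Under the protocol, an abnormality on any ECG up to 30 days after the last dose belongs in the summary. Under the SAP's own definition of on-treatment ECG data, the count ends 28 days sooner.

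A shorter window can only leave the count equal or lower, so any error makes the regimen look safer. In the same report, adverse events (SAP 7.1.5.1) and graded laboratory abnormalities (SAP 7.2.2.1) run to + 30 days, so the incidences would not share a risk period.

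This matters more in Cohort 3 than it might elsewhere. Protocol Table 1-3 predicts a mean GS-331007 AUCtau of 111,000 ng•hr/ml, against 31,100 observed in Cohort 1, and protocol 1.9 acknowledges that safety experience at such exposures is slight.

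**Working it through.** The documents give no figure to reproduce. The check counts days on the SAP's own scale (FU day = collection date minus last dose date), then sizes the effect.

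**1. Inputs**
- Counting limits: FU day 2 (SAP 3.8.2) and FU day 30 (protocol 8.2.1.2 and 8.5).
- Post-treatment Week 4 ECG: day 28 ± 7, so FU days 21 to 35, which is 15 permitted days (SAP Appendix 1, footnote j).
- Early Termination ECG: within 72 hours of stopping (footnote c), so FU days 0 to 3 if stopping is dated from the last dose.
- Scheduled on-treatment ECGs: Weeks 4, 8 and 12 (SAP Appendix 1 and Table 3-2).
- Cohort 3 size: 15.

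**2. Which ECGs are counted**

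| ECG | Limit at + 2 days | Limit at + 30 days |
|---|---|---|
| Week 4, 8, 12 on treatment | counted | counted |
| Early Termination, FU days 0 to 2 | counted | counted |
| Early Termination, FU day 3 | not counted | counted |
| Post-treatment Week 4, FU days 21 to 30 (10 of 15 days) | not counted | counted |
| Post-treatment Week 4, FU days 31 to 35 (5 of 15 days) | not counted | not counted |

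The two rules differ over FU days 3 to 30, which is 30 − 3 + 1 = 28 days.

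**3. Weight of one subject**

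1/15 = 6.7 percentage points. Clopper-Pearson 95% intervals show the scale (the SAP plans none for this table): 0/15 = 0% (0 to 21.8), 1/15 = 6.7% (0.2 to 31.9), 2/15 = 13.3% (1.7 to 40.5).

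**4. Illustration of the shift in incidence**

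The documents give no rate of abnormality per ECG, so *p* is assumed. With independent ECGs and every Week 4 visit done by day 30, incidence is 1 − (1 − p)³ over three ECGs and 1 − (1 − p)⁴ over four:

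| p (assumed) | Three ECGs | Four ECGs |
|---|---|---|
| 2% | 5.9% | 7.8% |
| 5% | 14.3% | 18.5% |
| 10% | 27.1% | 34.4% |

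At p = 5% the gap is 0.05 × 0.95³ = 4.3 points. If Week 4 visits were instead spread evenly over the permitted 15 days, only 10/15 would qualify, and the gap would be 4.3 × 10/15 = 2.9 points. An abnormality that persists from an on-treatment ECG adds nothing at Week 4, because that subject is already counted.

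**The case against.** **The + 2 day rule is an inference.** No sentence in the SAP says that Table 15.11.9.1 stops at + 2 days. The limit comes from joining a table title to a definition written for visit windows. This stands as a limit on certainty. The inference is still the natural one. Appendix 2 titles the adverse event and graded laboratory tables as treatment-emergent, a term the SAP runs to + 30 days, and uses a different, defined term for ECG. The paragraph opening SAP 7 also names the data carried to + 30 days without naming ECG.

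**The data are not lost.** A reader might infer that post-treatment ECG findings disappear from the report. The documents do not support that. Listing 16.2.8.2.3.1 covers the overall ECG assessment for every subject, and with 15 subjects it can be read line by line. Under protocol 7.1.3, ECG abnormalities with signs or symptoms that meet the adverse event definition must be recorded as such, and they are then counted to + 30 days. Table 3-3 also gives ECG data an FU-4 window, although its footnote b names only vital signs and laboratory data, so FU-4 interval summaries are uncertain. This narrows the loss, but a listing is not the incidence the protocol named.

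**The Early Termination loss is small.** A reader might infer that the plan drops ECGs from subjects who stop for toxicity. It does so only from day 3 onward; Early Termination ECGs on days 0 to 2 are counted. Whether an ECG is required at that visit is itself unclear: the schedule marks one, but the list in protocol 6.7 does not.

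**Protocol 8.5 does not name ECG in its opening sentence.** That is true, but its summary rule covers all safety data, and both 8.1.2 and the synopsis treat ECG as a safety measure.

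**Nothing formal depends on the number.** The cohort is single-arm and descriptive, with no tests and no ECG threshold. This limits the consequence but does not resolve the conflict.

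**Conclusion.** The point holds in a limited form. The protocol's window for a primary safety endpoint is + 30 days. The only table that reports its incidence is, on the most natural reading, cut at + 2 days, and SAP 7.8 says nothing has changed.

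What goes uncounted is an abnormality first seen on FU days 3 to 30 and not reported as an adverse event. In practice this is mainly the post-treatment Week 4 ECG done by day 30. Each such subject is worth 6.7 points.

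The shift from 18.5% to 14.3% should not be read as a forecast. It is an illustrative upper-end case for an assumed 5% rate: it takes ECGs as independent within a subject, the off-drug rate as equal to the on-drug rate, and all Week 4 visits as done by day 30. Persistent abnormalities or later visits would shrink it. The conclusion concerns Cohort 3 only, since this SAP covers no other cohort.

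**What to change.** - **SAP 7.5:** describe Table 15.11.9.1 and say what counts as an ECG abnormality. Count subjects with an abnormality that is new or worse than baseline, using each subject's worst post-baseline ECG from first dose through last dose + 30 days, including FU-4 and any Early Termination ECGs. The baseline comparison is needed: without it, pre-existing abnormalities would count as emergent, unlike the protocol's rules for adverse events (8.5.2) and laboratory values (8.5.3).
- **Appendix 2:** retitle the table to match. If an on-treatment version is kept as well, label it supplementary.
- **SAP 3.8.2:** keep the + 2 day cut for by-visit labelling only.
- **SAP 7.8:** if the sponsor nevertheless keeps + 2 days for this count, declare it there as a departure from the protocol.
- **Early Termination visit:** reconcile the ECG marked in the schedule's ET column with the list in protocol 6.7, which omits it.

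The cost is a short definition in SAP 7.5, plus a date filter and a baseline comparison in one table. All the data are already collected. If the SAP is already final, its section 1 provides for recording the change in the CSR. The reported incidence may come out slightly less favourable.
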